11.0 STATISTICAL CONSIDERATIONS

11.1 Primary Objective

Joint pain will be assessed using “average pain” according to the BPI-SF. Enrollees must currently be taking AIs and must exhibit joint pain with a minimum BPI-SF average pain score of 4; scores of 4 to 10 are considered to reflect moderate to severe pain. (42) Patients will be stratified at randomization by the use of average baseline pain according to the BPI (4-6 vs 7-10) and prior taxane use (yes vs. no). The primary assessment time of 12 weeks, upon which power calculations are based, corresponds to completion of the intervention and allows cross-trial comparisons to be made with **S0927**, which is evaluating a different pharmacologic agent for treatment of AIMSS in the same patient population.

This study stipulates an $\alpha=0.05$ two-sided test, with an estimated 5% non-adherence (reducing the nominal effect size) and 15% dropout rate (increasing the total required sample size) at 12 weeks after randomization. (16, 43) In addition, the design will

incorporate a 10% contamination rate (which also reduces the nominal effect size) based on the assumption that a portion of the patients will not benefit from intervention based on joint pain with a different etiology that is not associated with AI treatment (this has a similar impact on power calculations as a “drop-in” rate).[\(44\)](#)

The proposed sample size incorporates adjustments for loss, non-adherence, and contamination. The power for the design will be a function of the difference detected and the standard deviation at 12 weeks after randomization.

Difference Detected: Although a difference of 2 points in the BPI has been identified as representing a clinically meaningful *individual* level difference, for power calculations assessing group-level differences, we will test a smaller effect. [\(45\)](#) Specifically, an incremental difference in pain reduction due to duloxetine over placebo of about 1.0 points at 12 weeks has been repeatedly found in the setting of fibromyalgia. [\(43,46\)](#)

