Standard Deviation: Multiple studies of AI-induced joint pain have found the standard deviation for BPI “average pain” at follow-up on placebo to be about 2.0 to 2.5 points. [\(47,8\)](#) The design assumes a common standard deviation between arms; a similar standard deviation has been observed in a pilot study of duloxetine. [\(16\)](#) We assume a SD of 2.3 points at 12 weeks for this study (the estimated average SD found in Arnold, Clin J Pain, 2009). [\(8\)](#)

For a 1.0 point difference and a 2.3 point SD at 12 weeks, with other parameters as specified above, 270 eligible patients would be required for 80% power under a two-arm normal design. Power will be higher with lower observed standard deviation or a larger observed difference.

The following considerations clarify the impacts of loss, non-adherence, and contamination on the sample size calculations:

- A two-arm normal design with $\alpha=0.05$ two-sided test and a 2.3 point SD to detect a difference of 1.0 points requires approximately 166 patients (83 per arm) for 80% power.
- An estimated 5% non-adherence and 10% contamination both reduce the nominal effect size, from 1.0 points to 0.85 points. This increases the required sample size to 230 total patients (115 per arm).
- To account for an estimated 15% dropout rate, the total required sample size must be further increased by 15%, as in $230/0.85 = 270$ total patients.

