6. Reduces depression as measured by the Patient Health Questionnaire (PHQ-9). Differences between the two arms of at least five points on the PHQ-9 at 12 weeks will be of interest. (57) Clinically meaningful change in PHQ-9 scores will also be based on $\frac{1}{3}$ to $\frac{1}{2}$ of a standard deviation. (57)
 7. Decreases analgesic use.
 8. Increases adherence to, and reduces the discontinuation rate for, AI therapy.
 9. Affects measures of pain interference.
 10. Reasons for treatment discontinuation will also be described.
- c. Interaction tests between treatment and stratification variables will be conducted to explore whether these factors are predictive of average pain scores.
 - d. A logistic regression analysis of responders will be conducted, where a response to intervention is defined as a reduction of 2 or more points in average pain according to the BPI. (50)
 - e. In addition, we will explore the relationship between the severity of arthralgias and degree of benefit from therapy in each of the treatment groups and inherited variants in genes responsible for duloxetine metabolism and activity (COMT, HTR3A, SLC6A2, SLC6A4, CYP1A2, CYP2D6) and aromatase (CYP19A1). Finally, we will explore the relationship between baseline and change in serum inflammatory cytokine levels with 12 weeks of treatment and the degree of benefit from therapy in each of the treatment groups.

For linear scales, secondary endpoints will be analyzed using multiple linear regression analyses including the baseline score as a covariate and the pre-specified stratification factors. For binary outcomes, logistic regression will be used.

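### Section 11.3 names no covariates for the logistic models, including the responder analysis, although it names baseline score and stratification factors for the linear ones

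*Combined protocol and SAP*

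**What the plan says.** The closing paragraph of section 11.3 sets the methods for secondary outcomes in two sentences. The first reads "For linear scales, secondary endpoints will be analyzed using multiple linear regression analyses including the baseline score as a covariate", and goes on to add the stratification factors. The second reads, in full, "For binary outcomes, logistic regression will be used".

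Item 11.3d covers the responder analysis: "A logistic regression analysis of responders will be conducted, where a response to intervention is defined as a reduction of 2 or more points" in BPI average pain. It names no covariates and no time point.

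Elsewhere the plan adjusts consistently:

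- Section 6.0 balances randomization on baseline BPI-SF item 4 (4-6 vs 7-10) and prior taxane use.
- Section 11.1 adjusts the primary mixed model for baseline average pain and the stratification factors.
- Item 11.3a does the same for the regressions at single time points.

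No other section supplies covariates for the logistic models, and none says that these models are unadjusted.

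**The concern.** The two sentences stand side by side and differ only in that one lists covariates. An analyst who follows the text fits treatment alone for responders, on the same BPI item that the primary model analyses with adjustment. An analyst who assumes that the list carries over fits something else. The two models estimate different odds ratios, so the reported figure depends on a choice that the plan does not record.

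Baseline can matter here. Patients enter with average pain of 4 to 10 (section 5.2d), and response is a fall of at least 2. A patient at 4 must reach 2 or less, whereas a patient at 10 need only reach 8. If baseline is related to the chance of response, leaving it out costs power. Leaving out the allocation factors also makes the responder analysis inconsistent with the design.

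**Working it through.** **1. The plan's own figures.** Section 11.1 gives no power for any binary outcome, so the check starts from the primary calculation, which supplies the evaluable number. The inputs are two-sided alpha 0.05, 80% power, and "For a 1.0 point difference and a 2.3 point SD at 12 weeks". The formula is n per arm = 2 × (1.960 + 0.842)² × SD² / difference².

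- Difference 1.0: 2 × 7.85 × 5.29 / 1.00 = 83.0. Rounded up this is 84 per arm, or 168 in total (plan: about 166).
- Difference 0.85: 83.0 / 0.7225 = 114.9, so 115 per arm and 230 in total. The plan agrees: "both reduce the nominal effect size, from 1.0 points to 0.85 points. This increases the required sample size to 230 total patients (115 per arm").
- Dropout: 230 / 0.85 = 270.6 (plan: 270).
- Ineligibility: 270 / 0.92 = 293.5, so 294 (plan: 294).

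The chain reproduces, and the point made here does not touch it. The number evaluable at 12 weeks is 230.

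**2. Responder power with and without covariates.** Each cell is 2,500 simulated trials of 230 patients, split evenly within the four strata.

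Inputs from the documents:
- mean baseline 5.5 and SD 1.1 (pilot, section 2.0, Table 1), with entry at 4 or more;
- follow-up SD 2.3 and effect 0.85 or 1.0 (section 11.1);
- response as a fall of at least 2 points (11.3d).

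Assumptions not in the documents:
- response judged at week 12;
- mean placebo fall of 1.5 points, giving about 50% placebo responders;
- baseline SD of 1.5 as a second value (both SDs apply before the cut at 4);
- baseline/follow-up correlation r from 0 to 0.55;
- half the patients with prior taxane, and no taxane effect.

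Scores were rounded to whole numbers from 0 to 10. The test was the Wald test from logistic regression. Power in %:

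| Effect | Baseline SD | r | Treatment only | + strata | + strata and baseline | Gain |
|---|---|---|---|---|---|---|
| 0.85 | 1.1 | 0.00 | 54.0 | 55.5 | 57.6 | 3.6 |
| 0.85 | 1.1 | 0.13 | 56.7 | 57.2 | 58.4 | 1.7 |
| 0.85 | 1.1 | 0.26 | 63.6 | 63.9 | 63.9 | 0.3 |
| 0.85 | 1.1 | 0.44 | 71.0 | 71.0 | 70.4 | -0.6 |
| 0.85 | 1.5 | 0.00 | 49.9 | 52.8 | 54.6 | 4.7 |
| 0.85 | 1.5 | 0.16 | 56.2 | 57.5 | 59.1 | 2.9 |
| 0.85 | 1.5 | 0.33 | 65.4 | 65.8 | 66.4 | 1.0 |
| 0.85 | 1.5 | 0.55 | 77.4 | 77.5 | 77.2 | -0.2 |
| 1.0 | 1.5 | 0.00 | 62.6 | 65.6 | 68.8 | 6.2 |
| 1.0 | 1.5 | 0.55 | 88.2 | 88.2 | 88.4 | 0.2 |

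The other cells at effect 1.0 gave gains between -0.3 and 3.7. Each power has a Monte Carlo standard error near √(0.5 × 0.5 / 2500) = 1 point. The models were fitted to the same simulated data, so the differences are more precise than that. With a 0.6-point taxane effect (effect 0.85, SD 1.5, r 0.16), power was 55.1% against 59.0%. A separate run at effect 0.85, also with a placebo fall of 1.5, gave 48-75% unadjusted against 54-75% adjusted, with the gain gone at r of about 0.35 or more.

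The pattern has a simple cause. Response is already a change from baseline. In the rows with r of 0.44 and 0.55, follow-up pain rises one point per point of baseline, so the change no longer depends on baseline and there is nothing left to adjust for.

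**3. Type I error.** With no treatment effect, rejection was 4.0% unadjusted against 4.1% adjusted (r 0.17), and 4.8% against 5.5% (r 0).

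**4. The odds ratio moves.** At effect 0.85, SD 1.5 and r 0, the mean log odds ratio goes from 0.515 to 0.616, a rise of 0.101 / 0.515 = 20%. The odds ratio goes from exp(0.515) = 1.67 to exp(0.616) = 1.85. At r 0.55 the log odds ratio goes from 0.723 to 0.732, about 1%. The adjusted (conditional) and unadjusted (marginal) odds ratios are different quantities.

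**5. Which binary outcomes have a baseline.** The Global Ratings of Change are not among the initial-visit questionnaires in section 7.2a and begin at Day 15 (section 7.2b). Item 11.3b.5 also groups them in three classes. Discontinuation of AI therapy has no baseline value, since every patient enters on an AI (section 5.2b). Only the stratification factors can be used for these.

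**The case against.** The strongest reply is that the plan is silent and does not exclude covariates. The primary model, the time-point regressions and the linear secondary analyses are all adjusted, so the sentence on binary outcomes may simply be short. That stands. A reader might infer that the plan prescribes an unadjusted responder analysis and disregards the stratification factors. The documents do not say so. What they show is that no covariates are named.

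The second reply is that the loss is small and can be nil. That also stands: the gain is at most about 6 points, and there is none once the baseline/follow-up correlation is moderate. The documents do not give that correlation. For the same reason they do not support the inference that baseline pain strongly determines response.

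The third reply is that adjustment is not without consequence, because it changes the odds ratio being estimated. This is right, and the plan should say which one it reports.

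Finally, the responder analysis is not among the objectives in sections 1.1 to 1.3, nor is it the primary or main secondary outcome in sections 10.1 and 10.2. This limits the importance of the point. It does not remove the gap, because under either reading the model for 11.3d is not fully specified.

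**Conclusion.** The point holds as a small improvement to a secondary analysis. Section 11.3 names covariates for linear outcomes and none for logistic models, although the design balances on baseline pain and taxane use and the primary model adjusts for both. Carried out as written, the responder test may give up roughly 0 to 6 percentage points of power with 230 evaluable patients. The upper end needs little or no correlation between baseline and follow-up pain. The loss disappears at a correlation somewhere around 0.35 to 0.45. These figures rest on an assumed placebo fall of 1.5 points and on the assumed baseline spread and correlation.

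It would go too far to say that the plan certainly loses power, or that adjusting has no other effect: some plausible settings show no gain, and the odds ratio changes its meaning. Type I error, the primary analysis and the sample size are not affected.

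**What to change.** Replace the last sentence of section 11.3 with wording such as:

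> Binary outcomes will be analysed by logistic regression that includes the stratification factors of section 6.0 and, where one exists, the baseline score of that outcome (for 11.3d, baseline BPI average pain as a continuous covariate). The adjusted (conditional) odds ratio will be reported, together with the responder proportion in each arm. Outcomes with no baseline value, such as the Global Rating of Change and discontinuation of AI therapy, will be adjusted for the stratification factors only.

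The cost is one short paragraph, settled before the data are unblinded for analysis. Baseline BPI and both stratification factors are already collected, so no new data, visits or patients are needed.

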11.4 Data and Safety Monitoring Committee

A Data and Safety Monitoring Committee will oversee the conduct of the study. The Committee consists of four members from outside of the SWOG, 3 SWOG members, 3 non-voting representatives from the National Cancer Institute (NCI), and the Group Statistician (non-voting). The members of this Committee will receive confidential reports every 6 months from the SWOG Statistical Center, and will meet at the Group's bi-annual meetings as necessary. The Committee will be responsible for decisions regarding possible termination and/or early reporting of the study. Given the anticipated rapid accrual to this protocol (≤ 2 years total), insufficient data will be available while the study is still accruing to conduct an interim analysis. Thus no formal interim analysis is planned.

12.0 DISCIPLINE REVIEW

There will be no formal discipline review for this study.

13.0 REGISTRATION GUIDELINES

13.1 Registration Timing

Patients must be registered prior to initiation of treatment (no more than five working days prior to planned start of treatment).

13.2 Investigator/Site Registration

Prior to the recruitment of a patient for this study, investigators must be registered members of a Cooperative Group. Each investigator must have an NCI investigator number and must maintain an "active" investigator registration status through the annual submission of a complete investigator registration packet (FDA Form 1572 with original signature, current CV, Supplemental Investigator Data Form with signature and Financial Disclosure Form with original signature) to the Pharmaceutical Management Branch, CTEP, DCTD, NCI. These forms are available on the CTSU Web site (enter credentials at <https://www.ctsu.org>; then click on the Register tab) or by calling the PMB at [name] Monday through Friday between 8:30 a.m. and 4:30 p.m. Eastern time.

Each investigator or group of investigators at a clinic site must obtain IRB approval for this protocol and submit IRB approval and supporting documentation to the CTSU Regulatory Office before they can enroll patients. Study centers can check the status of their registration packets by querying the Regulatory Support System (RSS) site registration status page of the CTSU member web site by entering credentials at <https://www.ctsu.org>.

Requirements for site registration:

- CTSU IRB Certification
- CTSU IRB/Regulatory Approval Transmittal Sheet

13.3 OPEN Registration Requirements

The individual registering the patient must have completed the appropriate SWOG Registration Worksheet. The completed form must be referred to during the registration but should not be submitted as part of the patient data.

OPEN will also ask additional questions that are not present on the SWOG Registration Worksheet. The individual registering the patient must be prepared to provide answers to the following questions:

- a. Institution CTEP ID
- b. Protocol Number
- c. Registration Step
- d. Treating Investigator
- e. Cooperative Group Credit
- f. Credit Investigator
- g. Patient Initials
- h. Patient's Date of Birth

- i. Patient SSN (SSN is desired, but optional. Do not enter invalid numbers.)
- j. Country of Residence
- k. ZIP Code
- l. Gender (select one):
 - Female Gender
 - Male Gender
- m. Ethnicity (select one):
 - Hispanic or Latino
 - Not Hispanic or Latino
 - Unknown
- n. Method of Payment (select one):
 - Private Insurance
 - Medicare
 - Medicare and Private Insurance
 - Medicaid
 - Medicaid and Medicare
 - Military or Veterans Sponsored NOS
 - Military Sponsored (Including Champus & Tricare)
 - Veterans Sponsored
 - Self Pay (No Insurance)
 - No Means of Payment (No Insurance)
 - Other
 - Unknown
- o. Race (select all that apply):
 - American Indian or Alaska Native
 - Asian
 - Black or African American
 - Native Hawaiian or other Pacific Islander
 - White
 - Unknown

13.4 Registration procedures

- a. All site staff will use OPEN to enroll patients to this study. OPEN is a web-based application and can be accessed at <https://open.ctsu.org>, or from the OPEN tab on the CTSU members' side of the website at <https://www.ctsu.org>, or from the OPEN Patient Registration link on the SWOG CRA Workbench.
- b. Prior to accessing OPEN site staff should verify the following:
 - All eligibility criteria have been met within the protocol stated timeframes. Site staff should refer to [Section 5.0](#) to verify eligibility.
 - All patients have signed an appropriate consent form and HIPAA authorization form (if applicable).

c. Access requirements for OPEN:

- Site staff will need to be registered with CTEP and have a valid and active CTEP-IAM account. This is the same account (user ID and password) used for the CTSU members' web site.
- To perform registrations on SWOG protocols you must have an equivalent 'Registrar' role on the SWOG roster. Role assignments are handled through SWOG.

Note: The OPEN system will provide the site with a printable confirmation of registration and treatment information. Please print this confirmation for your records.

- d. Further instructional information is provided on the OPEN tab on the CTSU members' side of the website at
- <https://www.ctsu.org>
- or at
- <https://open.ctsu.org>
- . For any additional questions contact the CTSU Help Desk at [name] or
- [contact]
- .

13.5 Exceptions to SWOG registration policies will not be permitted.

- a. Patients must meet all eligibility requirements.
- b. Institutions must be identified as approved for registration.
- c. Registrations may not be cancelled.
- d. Late registrations (after initiation of treatment) will not be accepted.

14.0 DATA SUBMISSION SCHEDULE

14.1 Data Submission Requirement

Data must be submitted according to the protocol requirements for **ALL** patients registered, whether or not assigned treatment is administered, including patients deemed to be ineligible. Patients for whom documentation is inadequate to determine eligibility will generally be deemed ineligible.

14.2 Master Forms

Master forms can be found on the protocol abstract page on the SWOG website (www.swog.org) and (with the exception of the sample consent form and the Registration Worksheet) must be submitted on-line via the Web; see [Section 14.3a](#) for details.

14.3 Data Submission Procedures

- a. SWOG institutions must submit data electronically via the Web using Medidata Rave® at the following url:

<https://login.imedidata.com/selectlogin>

1. If prompted, select the 'CTEP-IAM IdP' link.
2. Enter your valid and active CTEP-IAM userid and password. This is the same account used for the CTSU members' web site and OPEN.

- b. You may also access Rave® via the SWOG CRA Workbench. Go to the SWOG web site (<http://swog.org>) and logon to the Members Area using your SWOG Roster ID Number and password. After you have logged on, click on *Workbenches*, then *CRA Workbench* to access the home page for the CRA Workbench and follow the link to Rave® provided in the left-hand navigation panel.

To access the CRA Workbench the following must be done (in order):

1. You are entered into the SWOG Roster and issued a SWOG Roster ID Number,
2. You are associated as an investigator or CRA/RN at the institution where the patient is being treated or followed,
3. Your Web User Administrator has added you as a web user and has given you the appropriate system permissions to view data for that institution.

For assistance with points 1 and 2 call the Operations Office at [name]. For point 3, contact your local Web User Administrator (refer to the "Who is my Web User Administrator?" function on the swog.org Members logon page).

For difficulties with the CRA Workbench, please email [contact].

- c. Institutions participating through Cancer Trials Support Unit (CTSU) please refer to the CTSU Participation Table on [Page 4](#).

14.4 Data Submission Overview and Timepoints

- a. AFTER REGISTRATION BUT PRIOR TO BEGINNING PROTOCOL TREATMENT:

Submit baseline whole blood for DNA and blood for serum biomarkers as outlined in [Section 15.1](#). The SWOG Specimen Tracking System must be used for specimen submission.

- b. WITHIN 7 DAYS OF REGISTRATION:

Submit the following:

S1202 Onstudy Form

S1202 Cover Sheet for Patient-Completed Questionnaires

S1202 Brief Pain Inventory Short Form (BPI-SF)

S1202 Western Ontario and McMaster Universities Osteoarthritis (WOMAC) Index (Version 3.1)

S1202 Modified-Score for the Assessment and Quantification of Chronic Rheumatoid Affections of the Hands (M-SACRAH)

S1202 FACT-ES Trial Outcome Index (Version 4)

S1202 Patient Health Questionnaire-9 (PHQ-9)

Institutional surgical pathology report to confirm diagnosis of ER/PgR status

c. WITHIN 14 DAYS OF DAY 15, 43, 85 STUDY ASSESSMENTS:

Submit the following:

S1202 Treatment Form

S1202 Adverse Event Summary Form

S1202 Supplemental Agents Reporting Form

S1202 Cover Sheet for Patient-Completed Questionnaires

S1202 Brief Pain Inventory Short Form (BPI-SF)

S1202 Western Ontario and McMaster Universities Osteoarthritis (WOMAC) Index (Version 3.1)

S1202 Modified-Score for the Assessment and Quantification of Chronic Rheumatoid Affections of the Hands (M-SACRAH)

S1202 FACT-ES Trial Outcome Index (Version 4)

S1202 Global Ratings of Change in Joint Pain and Stiffness

d. WITHIN 14 DAYS OF DAY 43 AND 85 ASSESSMENTS:

In addition to the forms listed in [Section 14.4c](#), submit the **S1202** Patient Health Questionnaire-9 (PHQ-9)

e. WITHIN 14 DAYS OF DAY 85 ASSESSMENT:

In addition to the forms listed in [Sections 14.4c](#) and [14.4d](#), submit the **S1202** Patient Treatment Satisfaction Form

f. AT THE DAY 85 STUDY ASSESSMENT:

Submit blood for serum biomarkers as outlined in [Section 15.1](#). The SWOG Specimen Tracking System must be used for specimen submission.

g. WITHIN 14 DAYS OF THE DAY 99 TELEPHONE CALL TO PATIENT:

Submit the **S1202** Adverse Event Summary

h. WITHIN 14 DAYS OF THE DAY 169 FINAL STUDY ASSESSMENT:

Submit the following:

S1202 Supplemental Agents Reporting Form

S1202 Cover Sheet for Patient-Completed Questionnaires

S1202 Brief Pain Inventory Short Form (BPI-SF)

S1202 Western Ontario and McMaster Universities Osteoarthritis (WOMAC) Index (Version 3.1)

S1202 Modified-Score for the Assessment and Quantification of Chronic Rheumatoid Affections of the Hands (M-SACRAH)

S1202 FACT-ES Trial Outcome Index (Version 4)

S1202 Global Ratings of Change in Joint Pain and Stiffness

i. WITHIN 14 DAYS OF REMOVAL FROM PROTOCOL INTERVENTION:

Submit the following:

Off Treatment Notice-Prevention Studies

Final **S1202** Treatment Form

Final **S1202** Adverse Event Summary

Final **S1202** Supplemental Agents Reporting Form

NOTE: If the patient goes off protocol intervention prior to Day 91 for any reason (see [Section 7.4](#)), the **S1202** Supplemental Agents Reporting Form and the patient-completed questionnaires should continue to be administered according to the protocol assessment schedule.

j. WITHIN 14 DAYS OF A DIAGNOSIS OF NEW OR RECURRENT CANCER OCCURRING UP TO DAY 169 ASSESSMENT:

Submit the Follow-up Form.

NOTE: If the patient was on protocol intervention at the time of new or recurrent cancer diagnosis then also submit the forms listed in [Section 14.4i](#).

k. WITHIN 4 WEEKS OF KNOWLEDGE OF DEATH OCCURRING UP TO 168 DAYS AFTER REGISTRATION:

If patient was on **S1202** protocol intervention, submit:

Notice of Death documenting death information

S1202 Treatment Form

S1202 Adverse Event Summary

S1202 Supplemental Agents Reporting Form

If patient was off **S1202** protocol intervention, submit:

Notice of Death documenting all death information

